8.2 DEFINITION OF BASELINE, STUDY VISITS, AND VISIT WINDOWS

Baseline will be defined as the last non-missing assessment prior to the first dose of IMP.

Summaries that show visit will be created using the visit reported in the eCRF. No visit reassignment will be done.

Study day is defined relative to the first dose of IMP. The first day of any IMP is considered Day 1. A minus (-) sign indicates days prior to the start of IMP (e.g., Day -5 represents 5 days before start of treatment. There is no Day 0. The relative study day for a specific visit is calculated as (Visit Date – Date of First Dose +1).

8.3 HANDLING OF MISSING DATA

All available efficacy and safety data collected for the study will be included in data listings and/or summary tables. Every effort will be made to obtain required data at each scheduled evaluation from all subjects enrolled. Rules for deriving efficacy endpoints will utilize imputation rules as specified in the efficacy analysis section. Sensitivity analyses will be performed to ensure that results of the primary efficacy endpoint are robust and not explained by missing or incomplete data. Worst-case assumptions will be applied to subjects who do not have OM assessments during the study period. Where necessary, missing assessments of OM will be imputed using multiple imputation procedures. Select exploratory sensitivity analyses will be conducted to ascertain the effect, if any, of these methods. No other missing data will be imputed.

Any imputation of missing or incomplete data will be flagged in the analysis data sets. The original value will be kept for traceability.

Incomplete dates imputation.

The following rules will be applied for AEs and concomitant medications with incomplete dates:

- If Day is missing for Start Date and Month and Year are the same as Month and Year for the First Dose of IMP Date, then Start Date equals First Dose of IMP Date.
- If Day is missing for Start Date and Month and Year are not the same as Month and Year for the First Dose of IMP Date, then impute Day 1 of the Month.

- If Day and Month are missing for Start Date and the Year is the same as the Year for the First Dose of IMP Date, then Start Date equals First Dose of IMP Date.
- If Day and Month are missing for Start Date and the Year is less than Year for the First Treatment Date, then impute July 1st of the Year.
- If Day and Month are missing for Start Date and the Year is greater than Year for the First Treatment Date, then impute January 1st of the Year.
- If the entire Start Date is missing, set it equal to First Dose of IMP Date.

No imputation for the end date of AEs will be done. However, the end date of concomitant medications will be imputed as the last day of the month if only the day is missing, and as December 31st of the year if both the day and the month are missing. The above imputation is needed to properly identify treatment-emergent adverse events (TEAEs) and prior/concomitant medications.

Other missing data imputation.

Missing OM data will be replaced using various algorithms, discussed in detail in Section 8.7.1 of this SAP.

No other missing data will be imputed.

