8 ADVERSE EVENT REPORTING

Throughout the study, AEs will be recorded in the source documents and transcribed onto the appropriate pages of the eCRF regardless of whether the AEs are considered treatment-related. All AEs with onset dates from signature of the ICF through the end of the short term follow-up phase will be recorded as an AE on the eCRF. All SAEs with onset dates from signature of the ICF through the end of the short term follow-up phase must be recorded following the guidelines in Sections 8.6, 8.7, 8.8, 8.9 and 8.10. Any AE that occurs at any time after completion of the study, which the investigator considers to be related to

This document contains confidential information. It is intended solely for the use of the principal investigator, co-investigators, staff, appropriate institutional review boards or ethical committees, and other required regulatory bodies.

study drug, must be reported.

Conditions existing prior to screening will be recorded as part of the subject's medical history. To avoid confusion, the AE should be recorded in standard medical terminology. The Investigator is responsible for assessing the relationship of AEs to the IMP (Section 8.3).

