8.6.3 PRIOR AND CONCOMITANT MEDICATION

Prior chemotherapy will be summarized by treatment arm and overall for SAF and ITT populations.

Medications will be coded with the WHO Drug Dictionary (WHO DD Mar 2017). Concomitant medications will be summarized stratifying by Anatomical Therapeutic Chemical (ATC) Classification System level 2 and 4 codes (ATC2 and ATC4). A medication will be considered to be concomitant if its end date is after the first date of IMP or its start date is on or after the first date of IMP and before the end of Short Term Followup. Medications with missing end date will also be considered concomitant. A medication with end date prior to the first date of IMP will be considered prior.

Separate listings for prior chemotherapy, prior medications, and concomitant medications will be generated. Any on-study surgeries or procedures will be listed.

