8.8.2 ADVERSE EVENTS

All AEs will be coded by PT and SOC using MedDRA version 19.0 or higher. The NCI-CTCAE (Version 4.03) will be used to grade both clinical and laboratory AEs.

The incidence of TEAEs will be summarized by treatment group and tabulated by SOC and Preferred Term (PT). A TEAE is defined as an AE that first occurs or worsens in severity on or after the first dose of the IMP until end of short term follow-up. Summary tables will include all TEAEs. Incomplete starting dates of AEs will be imputed using the rules from section 8.3 of this SAP. TEAEs will be further summarized by severity (grade) and relatedness to IMP. Each AE (based on PT) will be counted only once for a given

subject. If the same AE occurs on multiple occasions, the highest severity and strongest relationship will be assumed. If 2 or more AEs are reported as a unit, the individual terms will be reported as separate events. AE severity will not be imputed if missing.

Summaries and by-patient data listings of TEAEs, AEs leading to death, SAEs, and AEs leading to discontinuation will be provided. The by-patient AE data listings will include onset and resolution dates, verbatim term, PT, treatment, severity (grade), relationship to treatment, action taken for the event, and outcome. All the deaths, including those reported during the long-term follow-up period, will be listed with the primary causes.

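### Three of the six SAP 8.3 start-date rules ignore the end date, so an adverse event that ended before dosing can be counted as treatment-emergent

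*SAP*

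**What the plan says.** SAP 8.3 (incomplete dates imputation) applies one set of start-date rules to adverse events and medications. Three rules place the start on the first IMP date:

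- where "Day is missing for Start Date and Month and Year are the same as Month and Year for the First Dose of IMP Date";
- where "Day and Month are missing for Start Date and the Year is the same as the Year for the First Dose of IMP Date";
- where nothing is known: "If the entire Start Date is missing, set it equal to First Dose of IMP Date".

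The other three do not use the first IMP date. Where only the day is missing and "Month and Year are not the same as Month and Year for the First Dose of IMP Date, then impute Day 1" of that month. A start known only to an earlier year becomes 1 July of that year, and one known only to a later year becomes 1 January. Adverse event end dates are not imputed. Medication end dates are imputed to the end of the month or year. The section gives correct identification of TEAEs and of prior and concomitant medications as the reason for these rules.

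SAP 8.8.2 uses the imputed starts and states: "A TEAE is defined as an AE that first occurs or worsens in severity on or after the first dose of the IMP" (up to the end of short-term follow-up). It contains no exclusion based on the end date.

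Under SAP 8.6.3 a medication is concomitant if it ends after the first IMP date, or if "its start date is on or after the first date of IMP" and before the end of short-term follow-up, or if its end date is missing. It is prior if it ends before the first IMP date.

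Protocol section 8 sets the collection window: "All AEs with onset dates from signature of the ICF through the end of the short term follow-up phase will be recorded".

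**The concern.** Placing an unknown start on the first dose date is a sensible conservative convention when nothing shows that the record was over before dosing. The difficulty arises when the end date does show that. Screening can last up to four weeks before randomization and adverse events are collected from consent, so events that begin and resolve before the first dose can be in the database. For those events the three rules override information that already settles the question, and they produce a start date later than the end date.

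Adverse event incidence is the first listed safety endpoint (Protocol 10.1.3, SAP 5.3). At stake is the accuracy of the TEAE tables, which would then contain some events that happened off drug. The same three rules also leave some medications with two conflicting classifications.

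**Working it through.** There is no planned figure to reproduce. The check applies the SAP's rules to dates.

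**Notation.** F = first IMP date, E = recorded end date, S* = imputed start.

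**Classification rules as written**

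- TEAE (SAP 8.8.2): S* ≥ F.
- Concomitant (SAP 8.6.3): E > F, or F ≤ S* < end of short-term follow-up, or E missing.
- Prior (SAP 8.6.3): E < F.

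**General result.** Under the three rules S* = F. If E < F, then S* − E = F − E > 0, so the start falls after the end. The TEAE condition S* ≥ F is met. For a medication, the concomitant condition on the start and the prior condition on the end are both met.

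**Illustration (assumed dates).** F = 20 June 2019 and E = 12 June 2019.

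| Start as recorded | S* | S* − E | AE counted as TEAE | Drug meets concomitant clause | Drug meets prior clause |
|---|---|---|---|---|---|
| June 2019, day missing | 20 Jun 2019 | +8 days | yes | yes | yes |
| 2019, day and month missing | 20 Jun 2019 | +8 days | yes | yes | yes |
| wholly missing | 20 Jun 2019 | +8 days | yes | yes | yes |
| May 2019, day missing | 1 May 2019 | before end | no | no | yes |
| 2018, day and month missing | 1 Jul 2018 | before end | no | no | yes |

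The first three rows are wrong for adverse events and contradictory for medications. The last two are handled correctly. The remaining rule concerns a start in a year later than the first dose, so it cannot apply to a record that ended before dosing.

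**With an end-date condition.** If E < F, require S* ≤ E. In the first three rows S* is then no later than 12 June, which is before 20 June: the event is not a TEAE and the drug meets only the prior clause. A record with a wholly missing start and no end date still has S* = F and stays treatment-emergent or concomitant, as now.

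**Boundary check for medications, unrelated to partial dates.** Take a start before F and E = F. Then E > F is false, S ≥ F is false, E is not missing, and E < F is false. No class applies.

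**The case against.** The best defence has four parts.

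- **Medications.** SAP 8.6.3 already uses the end date. A reader might infer that drugs stopped before dosing are planned to appear in the concomitant table. The text does not support that, because such a drug is expressly prior. What stands is that it also meets the concomitant clause, and nothing says which clause wins.
- **Scope.** A reader might infer that partial start dates in general go to the first dose. Only three of the six rules do this, and the others cannot misplace a record that ended before dosing.
- **Convention.** Imputing to first dose is conservative, and rightly so, when the end date is missing or falls on or after dosing. The criticism is confined to the missing end-date check.
- **Safeguards.** Sites record at Baseline all events since consent (Protocol 7.3.1), so pre-dose events are captured close to when they happened. Edit checks and queries address inconsistent data (Protocol 12.3). Imputations are flagged with original values kept (SAP 8.3), and listings show onset and resolution dates (SAP 8.8.2). Each preferred term counts once per subject, so a misplaced event adds to an incidence row only if that subject has no true TEAE with the same term.

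The safeguards make errors rarer and traceable. They do not alter the rule or correct the TEAE tables that it feeds.

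**Conclusion.** The point holds in a limited form. For adverse events, three stated rules give a result that the recorded data contradict whenever the end date precedes the first dose. For medications there is a double classification without stated precedence, and a separate gap for drugs that started earlier and ended on the first IMP day.

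The size cannot be given. The documents state neither how many start dates will be incomplete nor how many such events will have ended before dosing. A reader might try to size the problem from the share of pre-dose days that fall in the calendar month of first dose. That share describes every day-missing event starting before dosing, including those still ongoing at first dose, so it does not measure this fault.

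A reader might also infer a material dilution of the safety comparison. The documents do not support that either: the rules are the same in both arms and the number of misplaced events is unknown. The primary efficacy endpoint is not affected. This is a minor correction, worth making because the rule is wrong where it bites and the remedy has no drawback.

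**What to change.** 1. In SAP 8.3, add one condition to the three rules: if the end date (recorded, or imputed for medications) is before the first IMP date, the start is imputed no later than the end date, and the record is classed as pre-treatment (adverse event) or prior (medication). Records with no end date, or one on or after first dose, keep the current assignment.
2. In SAP 8.6.3, state that the prior rule takes precedence over the concomitant rule.
3. In SAP 8.6.3, change the concomitant end-date test from after to on or after the first IMP date, which closes the boundary gap.

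The cost is a few sentences and one programming condition, plus a one-word-level change to the medication test. SAP 8.1 allows the plan to be updated before database lock. No new data are needed.

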8.4 PATIENT DISPOSITION

The number of screened subjects will be summarized. For screen failures, the reason for screen failure will be summarized using counts and percentages.

The number of randomized subjects will be summarized along with the number and percentage of randomized subjects in each of the analysis populations, completing the study, withdrawing from the study and the primary reason for withdrawal by planned treatment regimen and overall. The number of deaths will be summarized by planned treatment regimen and overall. Cisplatin schedule, HPV status and geographical region will also be summarized.

Data listings of subject disposition, screen failures, and subject assignment to analysis groups will be created.

8.5 **PROTOCOL DEVIATIONS**

Deviations from the protocol will be recorded in CTMS (PRIMA) and reviewed on a monthly basis by Medical Monitors. A data listing of all protocol deviations will be created. Date, description and type (major/minor) of protocol deviation will be reported. Minor/Major classification will be established by way of manual review and final determination of major protocol deviations will be done before database lock.

8.6 **PATIENT CHARACTERISTICS**

8.6.1 BASELINE AND DEMOGRAPHIC CHARACTERISTICS

All baseline characteristics will be summarized by actual treatment regimen and overall for the Safety Analysis Set (SAF). The following parameters will be summarized:

- Age (years)
- Race
- Ethnicity
- Gender
- Childbearing potential for women (and reason for being of not of childbearing potential)
- Pregnancy test results
- Baseline Vital Signs (including Weight [kg], Height [cm], Temperature [°C], Respiratory Rate [bpm], Heart Rate [bpm], systolic blood pressure (SBP) [mmHg], diastolic Blood pressure (DBP) [mmHg], and Karnofsky performance status)
- Baseline Physical Examination

No hypothesis testing is planned for baseline characteristics, so the analysis will be purely descriptive.

Data listings of baseline characteristics and demographics will be created.

8.6.2 MEDICAL HISTORY

HNC history (primary diagnosis, tumor node metastasis (TNM) staging, presence of prior surgeries, presence of prior chemotherapy) will be summarized by treatment arm and overall for SAF and ITT populations.

Prior and concurrent medical conditions will coded using Medical Dictionary of Regulatory Activities (MedDRA) 19.0 dictionary or higher. Summaries of prior medical conditions will be prepared. The tables will be divided by system organ class (SOC) and preferred term (PT).

Prior surgical procedures and chemotherapy will be summarized by treatment arm and overall for SAF and ITT populations. Surgery summaries will be further divided by surgery name.

Listings will be prepared for HNC history, prior surgeries for HNC, for prior medical and surgical history, and for concomitant surgery and other procedures.

8.6.3 PRIOR AND CONCOMITANT MEDICATION

Prior chemotherapy will be summarized by treatment arm and overall for SAF and ITT populations.

Medications will be coded with the WHO Drug Dictionary (WHO DD Mar 2017). Concomitant medications will be summarized stratifying by Anatomical Therapeutic Chemical (ATC) Classification System level 2 and 4 codes (ATC2 and ATC4). A medication will be considered to be concomitant if its end date is after the first date of IMP or its start date is on or after the first date of IMP and before the end of Short Term Followup. Medications with missing end date will also be considered concomitant. A medication with end date prior to the first date of IMP will be considered prior.

Separate listings for prior chemotherapy, prior medications, and concomitant medications will be generated. Any on-study surgeries or procedures will be listed.

8.7 EFFICACY ENDPOINTS AND ANALYSIS

8.7.1 ANALYSIS OF PRIMARY EFFICACY ENDPOINT

The duration of severe OM (WHO grade 3 or 4) will be calculated as the number of days from the onset of severe OM (first time a WHO grade 3 or 4 is observed) to the day when severe OM has resolved (first time WHO grade 2 or less is observed after last WHO grade 3 or 4). This calculation allows for fluctuation in severity grades and considers separate episodes of SOM to be additive. Durations of 0 will be assigned to subjects who do not experience severe OM, even if the subject was not followed for the full planned period. Any subject who dies or withdraws prior to resolution of severe OM (i.e., with grade 3 or 4 at last assessment) will be assumed to have severe OM for the remainder of the observation period. In these cases, duration will be calculated as the number of days from the first onset of severe OM (WHO grade 3 or 4) until the end of Short Term Follow-up phase which will be taken as Week 13 (Day 91 relative to start of CRT). All available OM assessments will be used to derive efficacy endpoints, including WHO grades recorded during the treatment phase and the short-term follow-up period.

The intent of the primary statistical analysis is to test the superiority of AG013 over placebo in reducing the duration of severe OM. The null hypothesis is that the AG013 and placebo groups have the same duration (in days) of severe OM. The alternative hypothesis is that the duration of severe OM in the two treatment groups is different.

The generalized CMH method, stratified by cisplatin regimen (weekly versus tri-weekly), by HPV status (positive versus negative) and region (US versus Europe), will be used for the primary efficacy analysis. In case of erroneous stratification at baseline, the corrected stratification data will be used for the analysis. Standardized mid-ranks (also known as modified ridit scores) will be used for the test statistic. This generalized CMH test follows a chi-square distribution with 1 degree of freedom. The efficacy analysis will be performed in the ITT, mITT, and PP populations, with the ITT designated as primary. Below is the sample code that performs this analysis:

```
proc freq
```

```
data=test;
tables STRATUM*TRTPN*OM_DURATION / CMH SCORE=MODRIDIT;
run;
```

The effect of treatment on the primary efficacy endpoint will be examined within subject subgroups defined by region (US vs Europe), cisplatin regimen, HPV status and baseline disease characteristics (primary cancer diagnosis for 3 subcategories: oral cavity, oropharynx and all other). Descriptive summary statistics will be used for this purpose.

The following sensitivity analyses will be performed using alternative methods for the analysis of duration of severe OM in the ITT, mITT, and PP populations:

- Repeat the primary analysis using the worst adjacent imputation strategy for gap days, replacing the days without a value with the worst value between the closest previous and following values.
- Repeat the primary analysis but using imputation for missing data. For subjects with unresolved SOM, use the median value for subjects in the same treatment group with at least that duration. For subjects without severe OM but with incomplete follow-up (i.e., discontinued before the end of the active treatment period with no short-term follow-up OM assessments), use the median duration among patients in the same treatment arm who were free of severe OM for at least that length of follow-up.
- Calculate severe OM duration as the total number of days a subject has a grade 3 or 4 mucositis from the start of CRT until the end of the short-term follow-up phase, with last observation carried forward (LOCF) imputation (so, the OM grade at a day without assessment is considered to be the same as at the closest previous valid assessment).
- Same as the above, but using the worst adjacent imputation strategy for gap days (i.e. replacing the missing value with the worst value between the closest previous and following values).
- Repeat the primary analysis but using only the period from start of CRT to the actual last day of CRT to define duration of severe OM.

Listings of individual WHO OM grades and calculated primary endpoint values will be created.

The distribution of OM severity grades at each visit will also be displayed. These summary tables will present the number and percentage of patients per OM grade at each visit, by treatment group, for the ITT, mITT, and PP populations.

